5.4 IMP ACCOUNTABILITY

The investigator or delegate will confirm receipt of all shipments of the IMP in writing using the receipt form(s) provided by the sponsor or vendor.

Assignment of ZX008 or placebo to the subject will be handled through an interactive voice randomization (IVR)-or Interactive Web Response (IWR) platform. The investigator or delegate will be required to register the subject through IVR/IWR and all study medication will be assigned to the subject through the IVR/IWR. The IVR/IWR will also maintain a log of all received and dispensed medication.

All supplies must be accounted for throughout the study using the drug accountability form

ZX008 (Fenfluramine Hydrochloride)
ZX008-1601 Clinical Study PA 4.0 (Japan) 25 July 2022

provided by the sponsor before the start of the study. Drug accountability is the process of documenting all aspects of IMP receipt, storage, use, and disposition so that a full accounting of each unit can be made. This includes administration, and return and/or destruction of IMP. At the end of the study, the dated and signed (by the investigator or delegate, eg, pharmacist) original drug accountability form must be retained at the study site as verification of final drug accountability.

Records for the delivery of the IMP to the study site, the inventory at the study site, the use by each subject (use by subject will be documented in the subject diary), and the destruction or return of the IMP to the sponsor must be maintained by the investigator (or delegate). The records will include dates, quantities, batch numbers, and unique code numbers assigned to the IMP and to the subjects. The investigator must maintain records documenting that subjects were provided with the doses of the IMP specified in this study protocol. Furthermore, the investigator must reconcile all IMPs received from the sponsor. The investigator must provide reasons for any discrepancies in drug accountability. Forms will be provided by the sponsor to ensure standardized and complete drug accountability.

5.5 TREATMENT ADMINISTRATION

5.5.1 Part 1: Randomization

Upon completion of the Baseline Period in Part 1, subjects who qualify for the study will be randomized (1:1:1) in a double-blind manner to receive 1 of 2 doses of ZX008 (0.2 mg/kg/day, 0.8 mg/kg/day; 30mg/day maximum [0.5 mg/kg/day; 20 mg/day maximum for subjects taking concomitant STP]) or placebo. The randomization will be stratified by weight (<37.5 kg, ≥37.5 kg) to ensure balance across treatment arms, with a target of at least 25% in each weight group. Subjects will be assigned a randomization number by the IWR system upon confirmation that subject qualifies for enrollment in the Titration Period. Once a randomization number is assigned to a subject, the site will record the subject's initials and identification number on the corresponding study drug bottles. Each bottle will contain the appropriate concentration and volume of liquid to administer the assigned treatment (ZX008 0.2 mg/kg/day, ZX008 0.8 mg/kg/day [or 0.5 mg/kg/day for subjects taking concomitant STP], or placebo). ZX008 and placebo will be identical, thus rendering the study drug and placebo indistinguishable. For each IMP bottle and randomization number assigned, the following information will be recorded on the drug accountability form: subject initials, unique bottle number, date each bottle is assigned, and drug used and unused during the study.

5.5.1.1 Blinding

The blinding scheme instituted for this study will ensure that the volume of study medication taken cannot be associated with the dose group, thus unblinding the study. This is achieved by random assignment of different concentrations of the ZX008 oral solution (1.25 mg/mL, 2.5 mg/mL, and/or 5 mg/mL) by the IWR system. The IWR system will instruct site personnel to the volume of oral solution to be administered based on that subject's weight. (Dose will be recalculated by the system based on weight once at the midpoint of the study.) During the Titration, Maintenance, and Taper/Transition Periods, the subjects and study personnel (investigators, clinical staff, personnel involved in data collection and analysis, the Medical Monitor, and the sponsor) will be blinded to the treatment allocation and to the concentration of

ZX008 (Fenfluramine Hydrochloride)
ZX008-1601 Clinical Study PA 4.0 (Japan) 25 July 2022

ZX008 oral solution. If an investigator feels the blind should be broken, he/she can do so when necessary for treatment decisions. However, the investigator should endeavor to discuss with the Medical Monitor or Sponsor's Medical Representative, if available. The blind should only be broken in the event the knowledge of whether the subject is on active study medication versus placebo is needed to determine course of medical treatment for the event. The subject will be discontinued from the clinical trial upon breaking of the blind and the decision whether the subject can enter Part 2 will rest with the Sponsor if the subject exited Part 1 prior to completion.

5.5.2 Part 1: Titration Period

The investigator (or delegate) will dispense IMP only to subjects included in Part 1 of this study following the procedures set out in this study protocol. Subjects will be required to stay in the clinic for monitoring of adverse reactions until the investigator determines it is safe to leave. Those considered by the investigator to need further monitoring will be hospitalized until the investigator determines they can be safely discharged.

Study medication will be administered as equal doses BID in the morning and in the evening approximately 12 hours apart. Each dose should be separated by a minimum of 8 hours and a maximum of 12 hours. A missed dose of study medication may be taken later up to 8 hours before the next scheduled dose; otherwise, the missed dose should not be given.

If the parent/caregiver is unable to administer the full dose due to spillage (eg, dose was spilled during measuring, subject spit dose out during administration), he/she should attempt to give the full dose noting the extra amount used to fulfill the dose. If the subject vomits within the first 15 minutes of administration the dose may be readministered. **Care must be taken not to overdose.** If the amount spilled is not known, the parent/caregiver should not give additional medication to avoid potential overdose.

Administration of the IMP will be based on the randomized dose and subject's weight (kg) at Visit 3 (Part 1; Study Day -1). At Visit 8 (Part 1; Study Day 43), if the subject's weight (kg) has changed $\pm 25\%$ of the weight at Part 1; Study Day -1, the IMP dose will be recalculated. Subjects should be dosed using the oral dosing syringe provided.

In order to maintain the blind across all dose groups in Part 1 ([Section 5.5.1.1](#)) and allow step titration to the high dose, the dose for each subject will be titrated starting with a dose of ZX008 0.2 mg/kg/day (or placebo equivalent) BID. After 4 days at this dose level (Study Day 5), subjects randomized to the ZX008 0.8 mg/kg/day (or 0.5 mg/kg/day for subjects taking concomitant STP) group will increase their dose to 0.4 mg/kg/day (maximum 30 mg/day or 20 mg/day for subjects taking concomitant STP) while doses in the other two groups will remain constant. On Study Day 9, the dose for the 0.8 mg/kg/day group (or 0.5 mg/kg/day for subjects taking concomitant STP) will increase to the target dose or a maximum of 30 mg/day (or 20 mg/day for subjects taking concomitant STP). The titration is expected to take a total of 14 days (Table 5). A new bottle of IMP will be started by the subject at each level of the titration step. See [Section 5.1](#) for more information about the volume of ZX008 or placebo to be administered. If a subject does not tolerate IMP during titration, slower titration may be considered after consultation with the Medical Monitor.

ZX008 (Fenfluramine Hydrochloride)
ZX008-1601 Clinical Study PA 4.0 (Japan) 25 July 2022

Table 5: Titration Algorithm for Part 1

| Randomized Group | Titration Step 1 Study Day 1-4 | Titration Step 2 Study Days 5-8 | Titration Step 3 Study Days 9-14 |
|---|-----------------------------------|------------------------------------|---|
| ZX008 0.2 mg/kg/day | ZX008 0.2 mg/kg/day | ZX008 0.2 mg/kg/day | ZX008 0.2 mg/kg/day |
| ZX008 0.8 mg/kg/day (0.5 mg/kg/day for subjects taking concomitant STP) | ZX008 0.2 mg/kg/day | ZX008 0.4 mg/kg/day | ZX008 0.8 mg/kg/day (0.5 mg/kg/day for subjects taking concomitant STP) |
| Placebo | Placebo | Placebo | Placebo |
| Note: maximum daily dose of ZX008 is 30 mg (20mg for subjects taking concomitant STP) | | | |

5.5.3 Part 1: Maintenance Period

After completion of the Titration Period, subjects will enter the Maintenance Period and continue to receive the randomized dose of ZX008 or placebo and be treated for an additional 12 weeks. Study medication will continue to be administered BID in the morning and in the evening, approximately 12 hours apart. Each dose should be separated by a minimum of 8 hours and a maximum of 12 hours. A missed dose of study medication may be taken later up to 8 hours before the next scheduled dose; otherwise, the missed dose should not be given.

5.5.4 Part 1: Taper Period (for subjects not entering Part 2)

Subjects who complete the Maintenance Period and will not be continuing into Part 2, the open-label extension, and subjects who discontinue from Part 1 early, will be tapered off of study medication. Study medication will be administered as equal doses BID in the morning and in the evening approximately 12 hours apart. Each dose should be separated by a minimum of 8 hours and a maximum of 12 hours. A missed dose of study medication may be taken later up to 8 hours before the next scheduled dose; otherwise, the missed dose should not be given. IMP should be administered using the oral dosing syringe provided.

If the parent/caregiver is unable to administer the full dose due to spillage (eg, dose was spilled during measuring, subject spit dose out during administration), he/she should attempt to give the full dose noting the extra amount used to fulfill the dose. If the subject vomits within the first 15 minutes of administration the dose may be readministered. **Care must be taken not to overdose.** If the amount spilled is not known, the parent/caregiver should not give additional medication to avoid potential overdose.

In order to maintain the blind across all dose groups, all subjects who do not continue into Part 2 will participate in a blinded dose-tapering procedure over the course of 8 days. On the first day of the tapering period subjects in the ZX008 0.8 mg/kg/day group (or 0.5 mg/kg/day for subjects taking concomitant STP) will decrease to a dose of ZX008 0.4 mg/kg/day BID (maximum 30 mg/day or 20 mg/day for subjects taking concomitant STP). After 4 days at this dose level (Study Day 5), subjects in this group will decrease their dose to 0.2 mg/kg/day. Subjects in the ZX008 0.2 mg/kg/day group will decrease their dose to placebo on the first day of tapering while doses in the placebo group will remain constant throughout the tapering procedure. On Study Day 9, all subjects will stop taking study medication. The taper is expected to take a total of 8 days (Table 6). A new bottle of IMP will be started by the subject at each level of the taper step.

ZX008 (Fenfluramine Hydrochloride)
ZX008-1601 Clinical Study PA 4.0 (Japan) 25 July 2022

Table 6: Taper Algorithm for Part 1

| Randomized Group | Taper Step 1 Day 1-4 after study completion or early termination | Taper Step 2 Days 5-8 after study completion or early termination |
|---|--|---|
| ZX008 0.2 mg/kg/day | Placebo | Placebo |
| ZX008 0.8 mg/kg/day (0.5 mg/kg/day for subjects taking concomitant STP) | ZX008 0.4 mg/kg/day | ZX008 0.2 mg/kg/day |
| Placebo | Placebo | Placebo |

Note: maximum daily dose of ZX008 is 30 mg. (20mg for subjects taking concomitant STP)

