Part 1 will consist of a 4-week baseline, 2-week titration, 12-week maintenance, and 2-week taper or transition period. The 4-week Baseline Period will consist of the establishment of initial eligibility during a screening visit to include an assessment of cardiac parameters (ECG and ECHO), followed by an observation period where subjects will be assessed for baseline seizure frequency based on recordings of daily seizure activity entered into a diary. Upon completion of the Baseline Period, subjects who qualify for the study will be randomized (1:1:1) in a double-blind manner to receive 1 of 2 doses of ZX008 (0.2 mg/kg/day, 0.8 mg/kg/day; maximum dose: 30 mg/day [or 0.5 mg/kg/day, maximum 20 mg/day, for subjects taking concomitant stiripentol (STP)]) or placebo. Randomization will be stratified by weight (<37.5 kilograms [kg], ≥37.5 kg) to ensure balance across treatment arms, and at least 25% of subjects will be in each weight group. All subjects will be titrated to their blinded randomized dose over a 2-week Titration Period. Following titration, subjects will continue treatment at their randomly assigned dose over a 12-week Maintenance Period. Total treatment time from the beginning of the Titration Period through the end of the Maintenance Period is 14 weeks. Subjects will have ECG and ECHO assessments at weeks 6 and 14 during the Maintenance Period. At the end of the Maintenance Period (or early discontinuation), all subjects will undergo a blinded 2-week taper or transition period (Post-Dosing Follow-Up) depending on whether they exit the study or are enrolled in Part 2, the long-term open-label extension, respectively. A follow-up ECG and ECHO will be performed 3-6 months after study drug discontinuation for early termination, or for those subjects who complete the study but do not enter the open-label extension part. If there are any findings at the 3-month post-dose follow-up, a second follow-up will be repeated at 6 months and then every 3 months until resolved or stabilized.

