In Part 1 all subjects will receive ZX008 or matching placebo for up to approximately 16 weeks (Titration Period=2 weeks; Maintenance Period=12 weeks; Taper/Transition Period=2 weeks). At the end of the 12-week Maintenance Period, eligible subjects may enroll into Part 2, the open-label extension, after completing a 2-week transition period with blinded study medication. Subjects who enroll in Part 2 will have the option to receive ZX008 for up to 72 months (plus a 2-week taper at the end of the open-label extension), or until ZX008 is approved in the subject's country of residence and listed on a patient's health plan formulary, whichever comes first. Subjects who do not enroll in the open-label extension will undergo a taper off of study medication (doses will be administered in a blinded fashion similar to the titration, ie, doses will be decreased in 4-day increments). Follow-up cardiovascular safety assessments, including ECG and ECHO, will be performed following the last dose of study medication for all subjects that do not transition to commercial drug, regardless of whether they complete the entire study or terminate early, unless the subject was known to be taking placebo (ie, blind was broken). These follow-ups will occur 3 months following the last dose of study medication for any subject taking the medication for 2-13 weeks, and 3 and 6 months following the last dose for any subject taking the medication for >13 weeks. If there are any findings at a post-dose follow-up, another follow-up will be scheduled every 3 months until resolved or stabilized. Subjects who transition to commercially available ZX008 will not return for a follow-up after EOS/ET or a cardiac follow up after last dose but must have had an ECHO within 3 to 6 months before the transition date and will have follow-up ECHOs within required timeframe while on commercial drug supply.

Criteria for Evaluation:Efficacy:

The efficacy endpoints for Part 1 of the study are:

Primary Endpoint:

Percent change from baseline in the frequency of seizures that result in drops in the combined Titration and Maintenance Periods (T+M) in the ZX008 0.8 mg/kg/day group compared to the placebo group.

Key Secondary Endpoints:

- Change from baseline in the frequency of seizures that result in drops in T+M in the ZX008 0.2 mg/kg/day group compared to the placebo group.

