- Urine or serum pregnancy test for females of child-bearing potential
- Laboratory evaluation (serum chemistry, hematology, immunoglobulin, hormones, and urinalysis (urine for urinalysis may be collected at home, the night before the clinic visit, as long as collection procedures are followed to maintain sample stability))
- Urine or serum THC panel
- Whole blood CBD
- Collect plasma sample for AED pharmacokinetic evaluation (must document time of last dose)
- Tanner Staging for subjects >7 to 18 years of age ([Appendix 5](#))
- Collect, review, and dispense diary. Ensure diary is being completed daily; if diary compliance is low (i.e. $<90\%$), re-train parent/caregiver
- C-SSRS Since Last Visit Assessment ([Appendix 2](#))
- Clinical Global Impression – Improvement (assessed by parent/caregiver)

ZX008 (Fenfluramine Hydrochloride)
ZX008-1601 Clinical Study PA 4.0 (Japan) 25 July 2022

- Clinical Global Impression – Improvement (assessed by investigator)
- BRIEF ([Appendix 3](#))
- QOLCE ([Appendix 6](#))
- HADS ([Appendix 7](#))
- Zarit Caregiver Burden Inventory ([Appendix 8](#))
- Record AEs
- Record AESIs
- Collect used, partially used and unused study medication; perform drug accountability and review with parent/caregiver
- Dispense study medication for taper for subjects not continuing into Part 2.
- Dispense and administer study medication for transition for subjects continuing into Part 2. Subjects will be required to stay in the clinic for monitoring of adverse reactions until the investigator determines it is safe to leave. Those considered by the investigator to need further monitoring will be hospitalized until the investigator determines they can be safely discharged.

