6.1.3 POST-DOSE VISIT (CLINIC VISIT 13; STUDY DAY 113)

For subjects entering the Part 2 OLE Treatment Period, the subject will visit the clinic on Day 113, which will also be Part 2 Day 1. The procedures described in [Section 6.2](#) will be followed.

If the subject does not enter the Part 2 OLE Treatment Period (or discontinues from the study early), the subject will visit the clinic on Study Day 113 (or 14 days after the day of discontinuation). If necessary, Visit 13 may be conducted as a phone call, provided diaries and study medication are returned by this time. The following will be recorded/performed:

- Review current seizure activity (number/type/duration) from diary since previous visit
- AEs
- AESIs
- Concomitant medications
- Collect and review diary with parent/caregiver
- Collect used, partially used and unused study medication; perform drug accountability and review with parent/caregiver

6.1.4 CARDIAC FOLLOW-UP VISIT (CLINIC VISIT 14; 3 and 6 months after last dose)

If the subject completes the study but does not enter the Part 2 OLE Treatment Period or discontinues from the study early, the subject will return to the clinic after study drug discontinuation for follow-up cardiac testing. The timing and frequency of exams are in Table 10. Subjects on blinded medication who are found to have been on placebo are not required to participate in follow-up testing once the blind is broken. As the ECHO and ECG will be administered in a separate clinic than the pediatric neurology clinic, an asymptomatic subject receiving a follow-up ECHO and ECG does not require a physical examination.

Subjects with positive findings on safety evaluations at post-dose follow-ups should have

ZX008 (Fenfluramine Hydrochloride)
ZX008-1601 Clinical Study PA 4.0 (Japan) 25 July 2022

repeat examinations every 3 months until the finding is resolved or stable and unlikely to change, with reports submitted as AEs to the ZX008 safety database.

Table 10: Schedule of Post-Treatment Cardiac Follow-up for Part 1

| Parameter | Duration of Blinded ^a or Fenfluramine Treatment | | | Have had any cardiac sign or symptom regardless of the time on study drug ^b |
|--|--|------------------------------|------------------------------------|---|
| | Less than 2 weeks Cumulative | 2 and <13 weeks | >13 weeks | |

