10.1.1 DETERMINATION OF SAMPLE SIZE

The sample size for Part 1 Cohort A was estimated under the assumption that adding ZX008 at 0.8 mg/kg/day to current therapy will lead to a mean decrease in drop seizures that is 30 percentage points greater than adding placebo to current therapy. For example, if adding placebo leads to a 10% decrease in seizures, then adding the high dose of ZX008 would be expected to decrease seizures by at least 40%.

The variability expected in the trial was estimated from a Phase 3 trial of clobazam for patients with Lennox-Gastaut syndrome (Ng 2011) leading to an assumption that the SD is 50%. Other assumptions include an allowance for 20% dropouts between randomization and the start of the maintenance period.

Under these assumptions, and using a Wilcoxon rank-sum test to approximate the primary comparison between the ZX008 0.8 mg/kg/day and placebo groups, a sample size of 63 subjects per treatment group affords 90% power to detect a difference between groups that is significant at the $\alpha=0.05$ level. Assuming a 20% drop-out rate prior to the start of the maintenance period yields a requirement for an additional 16 subjects per group for a total of 79 subjects per treatment group. Similar calculations for the 0.2 mg/kg/day ZX008 group lead to a total required sample size of 237. The number of subjects randomized into Part 1 Cohort A is estimated to be approximately 250 due to the long baseline period.

The sample size of 10 to 15 subjects per treatment group in Cohort B is expected to provide a descriptive assessment of whether the treatment effect in Japanese subjects is similar that observed in Cohort A subjects from the rest of the world.

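### The Part 1 taper follows the randomized arm, not the dose being taken, so a high-dose subject who stops on Days 1–4 and is tapered has the dose doubled

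*Protocol*

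**What the plan says.** Section 5.5.4 applies the taper to Maintenance Period completers who do not enter Part 2, and also states that "subjects who discontinue from Part 1 early, will be tapered off of study medication". It sets no minimum time on drug. The synopsis agrees: "At the end of the Maintenance Period (or early discontinuation), all subjects will undergo a blinded 2-week taper or transition period". At the end-of-study or early-termination visit (Section 6.1.2.9) the site is told: "Dispense study medication for taper for subjects not continuing into Part 2".

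The taper is described as a reduction. Section 5.5.4 says the high-dose group "will decrease to a dose of ZX008 0.4 mg/kg/day BID (maximum 30 mg/day or 20 mg/day for subjects taking concomitant STP", and the synopsis (Duration of Treatment) says "doses will be administered in a blinded fashion similar to the titration, ie, doses will be decreased in 4-day increments". Table 6 lists its rows by randomized group, and its column headings cover early termination as well as completion. It has one row for the high-dose arm: 0.4 mg/kg/day on taper Days 1–4, then 0.2 on Days 5–8.

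On the way up, Section 5.5.2 says "the dose for each subject will be titrated starting with a dose of ZX008 0.2 mg/kg/day (or placebo equivalent) BID". Table 5 moves the high-dose arm to 0.4 on Days 5–8 and to its target only from Day 9. Slower titration may be agreed with the Medical Monitor if the drug is not tolerated.

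**The concern.** Table 6 assumes that every high-dose subject has reached the target dose. For a subject who leaves during titration, the scheduled first taper step equals or exceeds the dose already being taken. A taper that raises the dose after the decision to stop defeats its purpose, and the subject may be leaving because the drug was not tolerated.

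Leaving this early is foreseen. Section 10.1.1 states "Assuming a 20% drop-out rate prior to the start of the maintenance period yields a requirement for an additional 16 subjects per group", and the cardiac follow-up schedule (Section 6.1.4, Table 10) has a column headed "Less than 2 weeks Cumulative". Under Section 5.5.1.1 the investigator, the Medical Monitor and the sponsor are blinded to allocation, so whoever chooses the taper as the cautious route cannot see that the bottle may hold a higher dose.

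**Working it through.** No figure in the protocol needs reproducing here. The check sets Table 5 against Table 6 for the high-dose arm (mg/kg/day, below the daily caps).

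| Stop during | Dose at stop (Table 5) | Taper step 1 (Table 6) | Change |
|---|---|---|---|
| Days 1–4 | 0.2 | 0.4 | +100% |
| Days 5–8 | 0.4 | 0.4 | 0% |
| Day 9 onward | 0.8 (0.5 with STP) | 0.4 | decrease |

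**Comparison at equal dose.** Take two subjects, both on 0.2 mg/kg/day, who both stop on Day 3. Table 6 sends the one in the 0.2 arm to placebo and the one in the 0.8 arm to 0.4 mg/kg/day. Nothing in Section 5.5.4 separates them by dose reached.

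**Whole taper after a Days 1–4 stop.** Mean dose = (4 × 0.4 + 4 × 0.2) / 8 = 0.3 mg/kg/day. Against the 0.2 being taken, 0.3 / 0.2 = 1.5, or +50% on average over the 8 days.

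**Effect of the caps (30 mg/day; 20 mg/day with STP).**
- The doubling is complete up to 30 / 0.4 = 75 kg, or 20 / 0.4 = 50 kg with STP.
- The increase disappears only from 30 / 0.2 = 150 kg, or 20 / 0.2 = 100 kg with STP.
- At 20 kg: 0.2 × 20 = 4 mg/day rises to 0.4 × 20 = 8 mg/day.
- At 90 kg without STP: 0.2 × 90 = 18 mg/day; 0.4 × 90 = 36, capped at 30; 30 / 18 = 1.67, or +67%.

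**How many subjects.** The protocol gives no count of stops by day. Its planning allowance is 20% drop-out before the Maintenance Period: 0.20 × 79 = 15.8, stated as 16 per arm. If those stops were spread evenly over the 14 titration days (an assumption), 16 × 4 / 14 = 4.6 high-dose subjects would stop on Days 1–4 and another 4.6 on Days 5–8. With about 250 / 3 = 83.3 randomized per arm, the Days 1–4 figure is 0.20 × 83.3 × 4 / 14 = 4.8. If the 16 stops fell differently, the Days 1–4 number could lie anywhere from 0 to 16. These figures count stops, not tapers, and the number tapered will be lower.

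**The case against.** The strongest reply is that the situation will seldom arise. Section 4.5 lets the site investigator stop the drug at once instead of tapering, after discussion with the Medical Monitor where feasible. For someone with at most four days at the starting dose, that is the natural choice. Taper drug is dispensed at a clinic visit, and none is scheduled between Day -1 and Day 15; Visits 4 and 5 are phone calls. A rise from 0.2 to 0.4 on Days 1–4 therefore needs an unscheduled visit in that window. The 20% is a planning allowance that also covers people who never return for taper bottles. The higher dose is only the next titration step. The IWR may already handle the case, which cannot be seen from the protocol. Finally, this is Amendment 4.0 for Japan, whose visit table starts from extension Month 24, so Part 1 tapering appears to be over.

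Most of this stands as a limit on size. The headcount above is best read as a high-side illustration, and the Days 5–8 case is mild, because 0.4, then 0.2, then stop still descends overall. None of it corrects the table. The option to stop at once avoids the error only if it is chosen, and a blinded investigator has no cue to choose it for that reason. Slower titration can also hold a subject at 0.2 mg/kg/day beyond Day 4, which widens the window.

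**Conclusion.** The concern holds. As written, Table 6 raises the dose by 100% for four days (up to 75 kg, or 50 kg with STP) in a high-dose subject who is tapered from the first titration step, and gives no first-step reduction from the second. Both outcomes contradict the protocol's own description of the taper as a decrease, and no other text in Section 5.5.4 overrides the table.

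The conclusion is conditional on the taper being used and on the IWR following Table 6 literally. The practical effect is small: few subjects, a dose inside the studied range, and no bearing on the efficacy analysis. It is a dosing and safety error that should be fixed, not a threat to the trial's result.

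**What to change.** Key Table 6, the text of Section 5.5.4 and the IWR taper bottles to the dose being taken at discontinuation:

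| Dose at stop (mg/kg/day) | Step 1 (4 days) | Step 2 (4 days) |
|---|---|---|
| 0.2 | placebo | placebo |
| 0.4 | 0.2 | placebo |
| 0.8 (0.5 with STP) | 0.4 | 0.2 |

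Subjects on placebo stay on placebo. Everyone tapered still receives two blinded bottles over 8 days, so the blind is kept. The protocol already treats 0.2 mg/kg/day this way: Table 6 gives the 0.2 arm placebo, and Table 8, the open-label Part 2 taper, is keyed to current dose and lists no taper step at 0.2.

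The cost is a wording change and an IWR lookup that tracks the titration step reached, including under slower titration. No extra subjects or procedures are needed. If no Part 1 dosing remains, the useful step is retrospective: check which taper bottles the IWR assigned to high-dose subjects who stopped before Day 9 or during slowed titration, and take this into account when reading adverse events after those stops.
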